5.7.3 Severity

AEs will be assessed for severity (intensity) according to the clinical description provided in the CTCAE V.4.0 grading scale (Grade 1, Grade 2, Grade 3, Grade 4, or Grade 5). If an AE cannot be classified using CTCAE V.4.0 terminology, severity will be assessed using the following definitions listed in Table 5.

Table 5 Adverse Event Severity

Grade 1	Mild	Asymptomatic or mild symptoms; clinical or diagnostic observations only; intervention not indicated.
Grade 2	Moderate	Minimal, local, or noninvasive intervention indicated; limiting instrumental activities of daily living. ¹
Grade 3	Severe	Severe or medically significant but not immediately life-threatening; hospitalization or prolongation of hospitalization indicated; disabling; limited self-care activities of daily living. ²
Grade 4	Life-threatening	Life-threatening consequences; urgent intervention indicated.

Grade 5	Death	Death related to the AE.
----------------	--------------	--------------------------

- 1: Examples of instrumental activities of daily living are: using computers, phones, watching TV, reading, etc.
- 2: Examples of self-care activities of daily living are: bathing, dressing and undressing, feeding self, using the toilet, taking medications, etc.

5.7.4 Adverse Event Relationship

For each AE, the Investigator is required to assess the causal relationship (relatedness) between the administration of the study drug and the occurrence of the AE. The Investigator should use his or her clinical judgment and the following definitions to determine relatedness.

- **Unrelated:** Evidence exists that the adverse event has an etiology other than the study drug; and/or the AE has no plausible temporal relationship to administration of the study drug. For SAEs, an alternative causality must be provided (e.g., pre-existing condition, underlying disease, intercurrent illness, or concomitant medication).
- **Related:** There is a reasonable possibility that the event may have been caused by the study drug, including a plausible temporal relationship between AE onset and administration of the study drug, and the lack of a clear alternative etiology.

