3.5.1 Stopping Rules

The Stopping Criteria include:

1. The Principal Investigator (PI) and/or Medical Monitor conclude it is unsafe or not in the subject's best interest to continue.
2. IGF-I SDS \geq 3.0 SDS on two consecutive Day 8 time points despite dose adjustments
3. IGF-I SDS \geq 2.0 SDS on two consecutive Day 8 time points despite dose adjustments and accompanied by clinically meaningful drug-related AEs, as determined by the Investigator and the Medical Monitor.

Subjects meeting individual stopping criteria will be withdrawn from the study.

The Stopping Criteria for a dosing cohort or the study include the determination that the dosing cohort or the study is unsafe to continue.

STUDY POPULATION SELECTION

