An AE is any untoward medical occurrence in a clinical investigation subject administered a pharmaceutical product which does not necessarily have a causal relationship with this treatment. An AE can therefore be any unfavorable and unintended sign (including an abnormal laboratory finding, for example), symptom, or disease temporally associated with the use of a medicinal product, whether or not related to the medicinal product.

AEs may include increases in intensity or frequency of conditions or diseases that were pre-existing prior to study participation. Examples might include a subject in whom routine headaches become more severe or begin to occur more frequently. Medical or surgical procedures are not in and of themselves considered AEs, but if a condition or disease led to the

procedure, the condition or disease would be considered an AE unless it was present prior to entering the study and did not worsen after entering the study.

AEs may include sequelae of overdose, drug abuse/misuse reports, lack of efficacy, or occupational exposure. In the absence of associated sequelae, these events should be reported as Special Situations and not AEs. Situations in which an untoward medical occurrence has not occurred (e.g., hospitalization for elective surgery or social reasons) are also not considered AEs.

AEs will be reported using the terms in the CTCAE V.4.0 grading scale. A copy will be supplied in the Study Manual, and it can be found online at <http://evs.nci.nih.gov/ftp1/CTCAE> and <http://safetyprofiler-ctep.nci.nih.gov/ctc/ctc.aspx>.

Subjects entering the study with ongoing Baseline medical conditions should have their signs/symptoms graded according to CTCAE V.4.0 criteria. Increases in CTCAE V.4.0 grading from Baseline conditions (e.g., Grade 1 to Grade 2) will be considered adverse events.

A non-serious AE is any AE that does not meet the definition of a serious adverse event below.

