8.5 Safety

Safety analyses will be conducted on the safety population and will be summarized by cohort. Safety variables include AEs, clinical laboratory values, vital signs, and physical examination results.

AEs will be coded using MedDRA and will be summarized using the coded terms. Summaries of all treatment emergent adverse events (TEAEs), serious adverse events (SAEs) and Suspected, Unexpected Serious Adverse Reactions (SUSARs) will be presented. The incidence of CTCAE V.4.0 Grade 3 or 4 adverse events will be classified according to severity and relationship to study drug.

Observed and change from Baseline values for laboratory safety panels and vital signs will be summarized using descriptive statistics. Laboratory results will also be summarized and presented as shifts from Baseline.

No formal inferential analyses will be conducted for safety variables.

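### The relatedness definitions in Section 5.7.4 do not provide for drug contribution or aggravation, and they overlap, so safety summaries that use relatedness can be biased low or inconsistent

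*Combined protocol and SAP*

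**What the plan says.** Section 5.7.4 asks the investigator to apply clinical judgment along with two definitions.

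- **Unrelated** applies when either limb holds: "Evidence exists that the adverse event has an etiology other than the study drug; and/or the AE has no plausible temporal relationship" with dosing.
- **Related** rests on this test: "There is a reasonable possibility that the event may have been caused by the study drug", with plausible timing, "and the lack of a clear alternative etiology".

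Serious events placed in the Unrelated category carry a further requirement: "For SAEs, an alternative causality must be provided (e.g., pre-existing condition, underlying disease, intercurrent illness, or concomitant medication").

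Section 5.7 treats the worsening of a condition present before the study as an AE in its own right: "Examples might include a subject in whom routine headaches become more severe or begin to occur more frequently". A rise in CTCAE grade over a Baseline condition also counts. Section 5.7.6 adds that when a laboratory, vital-sign or examination change is due to worsening of a pre-existing condition, the condition itself is the reported AE.

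Relatedness is used in these places:

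- Section 8.5: Grade 3 or 4 AEs "will be classified according to severity and relationship to study drug", and a summary of SUSARs.
- Synopsis, Statistical Methods: the corresponding sentence can be read as applying the split to all AEs and SAEs too.
- Section 3.5.1, criterion 3: an IGF-I condition "accompanied by clinically meaningful drug-related AEs, as determined by the Investigator and the Medical Monitor".

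**The concern.** In an open-label extension in which every subject receives somavaratan, the relationship call is the only causality assessment that the protocol defines for each event. It has no concurrent control rate to set against it, so the rule behind the call matters more than it would in a controlled trial.

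The definitions treat causation as either the drug or something else. They have no wording for joint causation, yet Section 5.7 brings aggravated conditions into the AE data and Section 5.7.4 gives a pre-existing condition as its first example of an alternative cause. The protocol itself shows that competing causes can arise. The Introduction lists altered lipid metabolism among the manifestations of adult GHD, while Section 5.7.5 lists increased cholesterol among events reported as related in earlier adult trials. Sections 3.7 and 4.5 provide for underlying disorders and other hormone replacement.

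At stake are the summaries split by relationship and the SUSAR summary. Section 5.7.5 states that no specific events are at present considered expected with somavaratan. If the reference safety information named in Section 5.8 agrees, relatedness largely decides whether a serious event becomes a SUSAR.

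**Working it through.** The plan gives no figure to reproduce and no arithmetic applies. The check is to read the two definitions as logical conditions and to trace where the result is used.

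**Conditions in Section 5.7.4**

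- T: timing is plausible.
- P: there is a reasonable possibility that the drug caused the event.
- E: there is evidence of another etiology.
- C: there is a clear alternative etiology (C implies E).

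Read literally, Unrelated = E or not T, since either limb is enough. Related = P and T and not C.

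| Case | Related met? | Unrelated met? |
|---|---|---|
| (a) T, P, no E | yes | no |
| (b) T, P, E but not C | yes | yes |
| (c) T, P, C, drug also contributed | no | yes |
| (d) T, not P, no E | no | no |
| (e) not T | no | yes |

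Case (c) is a one-sided error: a drug contribution is recorded as Unrelated. Case (b) leaves the choice open, so two investigators can code the same event differently; its direction is undetermined. Case (d) is a formal gap of little practical weight.

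**Where a drug-aggravated condition falls.** If the underlying condition is taken as the etiology, as the example for serious events in Section 5.7.4 invites, the event is in case (c). If the worsening is judged as the event, as Section 5.7 permits, it is in (a) or (b). The wording does not settle which. Section 5.7.6 leans toward (c) for laboratory and vital-sign changes, because the reported term then names the condition.

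**Which outputs depend on the result**

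- All TEAEs and all SAEs (Section 8.5): inclusion does not depend on relatedness.
- Laboratory and vital-sign changes from Baseline, and laboratory shifts (Section 8.5): not affected.
- Grade 3 or 4 AEs by relationship (Section 8.5): affected.
- All AEs and SAEs by relationship (synopsis, on the wider reading): affected if that reading is intended.
- SUSARs (Section 8.5): affected.
- Stopping criterion 3 (Section 3.5.1): uses the term drug-related but does not cite Section 5.7.4, so the link is not stated.

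**Size.** The change in a related-event count would be the number of case (c) events, plus those case (b) events coded Unrelated. The documents give no AE count by competing cause, so this cannot be computed.

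**The case against.** The best reply is that the rule is not mechanical. Clinical judgment applies, only a clear alternative counts against Related, and the AE to be judged may be the worsening itself, so a drug-caused worsening can be called Related. The sentence can also be read with plausible timing and lack of a clear alternative as elements of reasonable possibility, not as separate bars. This stands to the extent that misclassification is possible, not certain. It does not remove the defect. Judgment is to be used together with the definitions, and evidence of another etiology still satisfies Unrelated. On the softer reading, case (c) can meet both definitions, which exchanges bias for inconsistency.

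A second reply is that underlying disorders must have been stable for 6 months, and other hormone therapy in naïve subjects for 3 months (Section 3.7), so new worsening is harder to blame on them. That may reduce the number of such events but does not say how to class those that occur.

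A reader might infer more than the documents support:

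- *That the primary safety tables as a whole are understated.* They are not: TEAEs and SAEs are summarized whatever their relatedness, and grade increases are recorded as AEs.
- *That stopping criterion 3 will fail to trigger.* It leaves the decision to the Investigator and the Medical Monitor without citing Section 5.7.4. Criterion 1, and several withdrawal reasons in Section 5.10, need no relatedness call, and a DSMB meets twice yearly.
- *That the relatedness call is the only causal information produced.* Baseline comparisons, PK and IGF-I data, and summaries by ADA status also bear on causality, though none is controlled.
- *That a percentage bias can be stated.* Any figure would rest on an invented incidence and an invented share of events with competing causes.

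**Conclusion.** The concern holds in a limited form. As written, Section 5.7.4 allows an event with a clear other cause and a drug contribution to be classed Unrelated, and it lets an event with partial evidence of another cause satisfy both categories. Summaries that use relatedness can therefore be biased low or coded inconsistently. This covers Grade 3 or 4 AEs by relationship and SUSARs, and possibly all AEs and SAEs by relationship if the wider reading of the synopsis is meant. The size is unknown and cannot be derived from the documents.

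The conclusion rests on two assumptions: that investigators follow the definitions at least in part, and that some events in this population have more than one plausible cause. The SUSAR element also depends on the reference safety information listing few or no expected events. An effect on stopping criterion 3 is plausible but not established. The defect lies in a stated rule, is cheap to correct, and should be corrected.

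**What to change.** Reword Section 5.7.4 so that the two categories are mutually exclusive and exhaustive:

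- **Related:** a reasonable possibility that the study drug caused, contributed to or worsened the event, whether or not another factor is present.
- **Unrelated:** no such reasonable possibility.

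Keep the recording of the alternative cause, and bring the eCRF completion guidelines into line.

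Separately, reconcile Sections 3.5.1 and 5.7.4 by stating whether drug-related in stopping criterion 3 means Related as defined in Section 5.7.4. If it does, rewording the definition also changes which events count under that criterion, and the sponsor needs to weigh this when the passages are reconciled.

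Costs: the text change is small, but related-AE counts may rise. The rationale for Version 2 shows that subjects are already participating, so a change now would mix two definitions. Either flag each AE by the definition in force when it was assessed and present the relationship summaries accordingly, or have the earlier AEs reassessed under the new wording.

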5.7.5 Related Adverse Events Experienced in Somavaratan AGHD Clinical Trials

Adverse events associated with somavaratan administration have been generally mild and transient and have been similar to those typically observed when rhGH is introduced in GHD patients. At this time, there are no specific events which are considered expected with somavaratan. However, adverse events reported as related to somavaratan treatment in GHD adults include:

- Injection site reaction (erythema, edema, pruritus, swelling, warmth, macule)
- Injection site pain
- Headache
- Myalgia
- Arthralgia
- Muscle fatigue
- Rash
- Erythematous rash
- Nausea
- Generalized edema
- Paresthesia
- Generalized pruritus
- Skin warmth
- Increased cholesterol (LDL, triglycerides)
- Increased lymphocytes

5.7.6 *Vital Signs, Physical Examination and Clinical Laboratory Adverse Events*

Laboratory abnormalities and changes in vital signs or physical examination findings are considered AEs only if they are determined to be clinically significant by the Investigator, result in withdrawal from the study, necessitate therapeutic intervention, or for some other reason the Investigator considers them clinically important. However, if any of these changes in laboratory, vital signs or physical examinations is attributable to a new disease or condition or a worsening of a condition pre-existing at study enrollment, the disease or condition itself shall be the reported AE, not the change in laboratory, vital sign or physical examination.

5.7.7 *Serious Adverse Events*

5.7.7.1 Definition

A serious adverse event (SAE) is defined by federal regulation as any AE occurring at any dose that results in any of the following outcomes: death, life-threatening AE, hospitalization or prolongation of existing hospitalization, a persistent or significant disability/incapacity, or a congenital anomaly/birth defect.

Medically significant events that may not result in death, be life threatening, or require hospitalization may be considered an SAE when, based upon appropriate medical judgment, they may jeopardize the subject and may require medical or surgical intervention to prevent one of the outcomes listed in this definition. Examples of such medical events include allergic bronchospasm requiring intensive treatment in an emergency room or at home, blood dyscrasias or convulsions that do not result in subject hospitalization, or the development of drug dependency or drug abuse.

5.7.7.2 Reporting Adverse Events, Pregnancies, and Serious Adverse Events

All AEs and SAEs, regardless of relatedness, that occur after informed consent until the end of the protocol-required post treatment follow-up period, must be reported as instructed. This also includes any events resulting from protocol-associated procedures performed after informed consent is signed.

All pregnancies (subjects and their partners) that occur from initiation of study medication until 4 weeks after last administration of study medication must be reported to the Sponsor's contracted pharmacovigilance vendor using the Pregnancy Data Collection form provided, as instructed.

All AEs and pregnancies (subjects and their partners) should be followed up until resolution if possible. If the AE has not resolved by the last day on study, the AE will be followed up until the Investigator and/or the Sponsor determines that the subject's condition is stable. However, the Sponsor may request that certain AEs be followed until resolution.

Investigators are not obligated to actively seek SAEs after study participation has concluded. However, if the Investigator learns of any post-study SAEs that are deemed relevant to the use of study medication, he/she should promptly document and report the event to the Sponsor.

All SAEs must be reported to Premier Research within 24 hours of discovery, by faxing the report to one of the following numbers or sending by email:

Attention: Pharmacovigilance

US Fax Number: [REDACTED]

US email: [REDACTED]

EU Fax Number: [REDACTED]

EU email: [REDACTED]

The written report should be submitted on the SAE form provided for this purpose. The report must include the Investigator's opinion as to whether the event is study drug-related. If the event is determined to be related to study drug, evidence to support this assessment must also be provided.

Complete reconciliation of SAEs often requires follow up and review of medications, terminology, treatments administered, start and stop dates, and subject discharge records. The study Investigator has ultimate responsibility to ensure complete review and follow up of SAEs as required.

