Appendix 2 Definition of Childbearing Potential and Contraceptive Requirements

The risks of treatment with somavaratan during pregnancy have not been evaluated. Please refer to the latest version of the Investigator's Brochure for additional information.

1) Definition of Female of Childbearing Potential

Women < 54 years of age with amenorrhea of any duration will be considered to be of childbearing potential unless they have had a hysterectomy, bilateral oophorectomy, or medically documented ovarian failure.

Women \geq 54 years of age with cessation of menses for \geq 12 months will not be considered to be of childbearing potential.

2) Contraceptive Requirements for Females

Female subjects of childbearing potential must agree to use a highly effective method of contraception from the enrollment visit through 30 days after the last dose of somavaratan. The Investigator should counsel subjects on appropriate methods for avoiding pregnancy during the study. These methods are recommended due to a low failure rate (<1% per year), and include the following:

Single methods: Copper or LNG Intrauterine Device (IUD), progesterone implant or injection, tubal sterilization*, or vasectomy with documented azospermia 3 months post-procedure

Combination methods: oral contraceptives plus barrier, transdermal patch plus barrier, vaginal ring plus barrier, diaphragm with spermicide plus condom

Abstinence is only considered an acceptable method of contraception if it is a pre-existing part of a subject's lifestyle. Symptom-thermal methods (basal body temperature, cervical mucous, or calendar/rhythm) or withdrawal are not considered adequate forms of contraception for the purposes of this study.

*Tubal sterilization via the Essure procedure is not considered a reliable form of contraception unless tubal blockage is verified by hysterosalpingogram (HSP) approximately 3 months after microinsertion. Prior to verification, another contraception method described above should be used.

3) Contraceptive Requirements for Male Subjects (and their female partners)

All male study participants must agree to consistently and correctly use a condom from Baseline until 90 days after administration of the last dose of study drug. If their female partner is of childbearing potential (as defined above), their female partner must use 1 of the methods of birth control listed above from the date of Screening until 90 days after administration of the last dose of study drug.

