Male subjects must agree to refrain from sperm donation for at least 90 days after the last dose of study drug.

4) Procedures to be Followed in the Event of Pregnancy

Subjects will be instructed to notify the Investigator if they or their partner become pregnant at any time during the study, or if they become pregnant within 30 days (90 days for partners of male subjects) of the last somavaratan dose. Subjects who become pregnant or who suspect that they are pregnant must report the information to the Investigator. Subjects whose partner has become pregnant or suspects she is pregnant must report the information to the Investigator. All pregnancies (subjects and their partners) should be followed up until resolution if possible.

Instructions for reporting pregnancy, partner pregnancy, and pregnancy outcome are outlined in Section 5.7.7.2.

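### The pregnancy reporting rule in Section 5.7.7.2 stops 4 weeks after the last dose, while Appendix 2 has partner pregnancies notified for 90 days and sends sites to that same section for reporting

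*Combined protocol and SAP*

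**What the plan says.** Section 5.7.7.2 sets one period for female subjects and for partners of male subjects. Pregnancies that "occur from initiation of study medication until 4 weeks after last administration of study medication must be reported" go to the sponsor's contracted pharmacovigilance vendor on the form provided.

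Appendix 2 sets two periods. Women of childbearing potential use highly effective "contraception from the enrollment visit through 30 days after the last dose of somavaratan". Female partners of male subjects who could become pregnant use one of the methods of "birth control listed above from the date of Screening until 90 days after administration of the last dose of study drug". Item 4 of the appendix applies the same lengths to notification: the Investigator is to be told of a pregnancy during the study, or "within 30 days (90 days for partners of male subjects) of the last somavaratan dose". It closes with a cross-reference: "Instructions for reporting pregnancy, partner pregnancy, and pregnancy outcome are outlined in Section 5.7.7.2".

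Three other provisions bear on the point:

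- Section 5.7.7.2 and Appendix 2 item 4 both ask that pregnancies in subjects and partners be followed to resolution where possible, with no time limit.
- Section 5.7.7.2 says that "Investigators are not obligated to actively seek SAEs after study participation has concluded". It goes on to say that an Investigator who does learn of a post-study serious event relevant to study drug should report it to the sponsor. Section 5.7.7.1 lists a birth defect among the serious outcomes.
- The follow-up contact at 60 ± 3 days (Section 6.1.8; Appendix 1, footnote 21) names adverse events and concomitant medications. It does not name pregnancy.

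**The concern.** The appendix with the longer period hands the site to the section with the shorter one, and no other text extends the vendor period. Take a male subject who tells the Investigator on day 60 that his partner has become pregnant. He has done what Appendix 2 asks. The Investigator who then opens Section 5.7.7.2 finds that the stated duty to report ended on day 28. Some sites would send the form and others would not, and both could defend what they did.

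Appendix 2 gives the reason to care: "The risks of treatment with somavaratan during pregnancy have not been evaluated". With nothing known, each exposed pregnancy is safety information that the sponsor needs, and the primary objective of this study is long-term safety. Uneven onward reporting would leave the sponsor's pregnancy data incomplete in a way that nobody could measure afterwards.

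**Working it through.** There is no sample-size or error-rate figure to reproduce, and the study plans no hypothesis test. The check compares the stated periods, counted in days after the last dose.

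**Inputs.** Vendor reporting: 4 weeks, women and partners alike (Section 5.7.7.2). Investigator notification: 30 days for women, 90 days for partners (Appendix 2, item 4). Follow-up contact: 60 ± 3 days (Section 6.1.8).

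**Vendor period in days.** 4 × 7 = 28.

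| Group | Notify Investigator to day | Report to vendor to day | Days notified but not reportable | Share |
|---|---|---|---|---|
| Female subjects | 30 | 28 | 30 − 28 = 2 | 2/30 = 6.7% |
| Partners of male subjects | 90 | 28 | 90 − 28 = 62 | 62/90 = 68.9% |

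**Sensitivity to the wording.** If a site reads 4 weeks loosely as 30 days, the gap for women disappears. The gap for partners is then 90 − 30 = 60 days, or 60/90 = 66.7%. The partner result does not depend on how the phrase is read.

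**What a question at the 60-day contact would cover.** The contact falls on days 57 to 63.

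- Women: 57 − 30 = 27 and 63 − 30 = 33. It comes 27 to 33 days after their 30-day period closes, so one question looks back over all of it.
- Partners: 90 − 63 = 27 and 90 − 57 = 33. It comes 27 to 33 days before their period closes, so that last stretch still depends on the subject coming forward.

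The documents do not give the number of men or of women of childbearing potential. The number of pregnancies affected therefore cannot be estimated.

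**The case against.** The strongest reply is that the cross-reference concerns method. On that reading Appendix 2 fixes the period, and Section 5.7.7.2 supplies the form and the recipient. A sensible site could read it so. But Section 5.7.7.2 states a period of its own, and that period explicitly includes partners. The reply shows that the text is ambiguous, not that it is consistent.

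A reader might go further and infer the following, none of which the documents support:

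- *Late pregnancies would not be followed up.* The request to follow pregnancies to resolution does not depend on a vendor report or on the 4-week limit.
- *A birth defect would have no route to the sponsor.* Investigators need not look for post-study serious events, but one that they learn of and judge relevant should be reported, with no time limit. This route does not cover a pregnancy that is ongoing or ends normally.
- *Day 60 is the only chance to find out.* Women are tested at quarterly visits and at the Termination Visit, unless tested in the 14 days before it. Section 6.1.8 also allows a return at about 3 months. That return is optional and names no pregnancy item, but it exists.
- *Pregnancy reporting should run as long as adverse event reporting.* Adverse events are those "that occur after informed consent until the end of the protocol-required post treatment follow-up period, must be reported as instructed", and follow-up is at about 60 days. The protocol treats pregnancies as a separate category, and nothing requires equal periods.
- *Thirty days of contraception is too short.* This point does not question that length, and the protocol refers to the Investigator's Brochure for further information on pregnancy.

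It also stands that the contact list in Section 6.1.8 does not forbid a pregnancy question. Its absence is an omission worth filling, not a contradiction.

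**Conclusion.** The two sections conflict as written. For partners of male subjects, 62 of the 90 notification days (69%) carry no stated duty to report onward. For women it is 2 of 30 days, which would not merit a change by itself. The conclusion rests on reading 4 weeks as 28 days and on taking the reporting sentence in Section 5.7.7.2 literally. The first assumption hardly affects the partner result. On the second, the looser reading leaves an ambiguity that the protocol should remove.

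The defect is confined to required reporting from the Investigator to the vendor. Notification, follow-up to outcome and the route for relevant post-study serious events all remain. No estimate, table or test in the analysis plan changes. The correction should be made because it concerns a safety rule and costs almost nothing.

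**What to change.** In Section 5.7.7.2, replace the single 4-week limit with 30 days after the last dose for female subjects and 90 days for partners of male subjects, matching Appendix 2. This alone removes the conflict. It is a wording change to one sentence and leaves Appendix 2 and the contraception requirements as they are.

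As a cheap addition, name pregnancy (women of childbearing potential) and partner pregnancy (male subjects) among the items asked at the 60-day contact, in Section 6.1.8 and in footnote 21 of Appendix 1. Remind male subjects there that notification runs to day 90. The cost is one or two questions at a contact that already takes place, with no new visit. Its limit is that partner pregnancies after the contact still depend on self-report.
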